8.2.6.1. Inclusion Criteria

Patients must have met the following diagnostic criteria to be included in the study:

- Diagnosis of congenital HA.
- Moderate disease classification $(1\% \le FVIII \le 5\%)$.
- Severe bleeding phenotype, defined as the patient previously having had spontaneous bleedings and for whom prophylaxis is required to prevent such bleeding or other life-threatening complications per physicians opinion or as otherwise noted in the data source (Srivastava et al., 2020). Severe bleeding phenotype will be captured using the following criteria:
 - Ongoing or previous prophylactic treatment with clotting FVIII infusions (Carcao et al., 2020) during the 12 months prior to the index date.
 Or:
 - Spontaneous bleeding, defined as a bleeding that was not caused by trauma or a medical procedure at any time in the past prior to the index date.

Or:

• An annualised bleeding rate (ABR) of \geq 2 events/year in the 12 months prior to the index date.

Based on previous studies on bleeding phenotypes among moderate patients with haemophilia where ABR≥2 is above the 3rd ABR quartile (Kloosterman et al., 2022) or at the median and above (den Uijl et al., 2014).

Due to the variability of reporting in the data sources, the exact operational definition of the severe bleeding phenotype will vary between data sources. Table 1 shows the different criteria that can be fulfilled in each specific database.

Hemlibra—F. Hoffmann-La Roche Ltd

Protocol BO44691, Version

Data source	Country	Spontaneous bleeding prior to index date	Prophylactic treatment 12 months prior to index date	Annualised bleeding rate 12 months prior to index date
UKNHD	UK	Low	Low	Derived (number of new bleeding episodes at follow-up)
FranceCoag	France	Good	Good	Derived (bleeding events)
HemoNED	Netherlands	Captured	Captured	Derived (date/time of bleed, cause, location, and severity)
ATHN dataset	US	Not collected	Good*	Derived (bleed events)*
WBDR	Multi-country	Good	Good	Derived (total number of bleeds at baseline and at follow-up visits)
CBDR	Canada	Collected	Good	Derived (total number of bleeds)

Table 1. Applicable criteria for severe bleeding phenotype in the considered data sources.

*Bleed events not specified as traumatic or spontaneous.

UKNHD, UK National Haemophilia Database; **UK**, United Kingdom; **ATHNdataset**, American Thrombosis and Hemostasis Network; **US**; United States; **WBDR**, World Bleeding Disorders Registry; **CBDR**, Canadian Bleeding Disorders Registry.

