Information from feasibility questionnaire or data dictionary: Good = >70% patients included in the disease registries have the required variable, Moderate = 40 - 70% patients with variable, Low <40% patients with variable, Captured = Not disclosed, Not collected = No patients with variable.

The above-mentioned inclusion criteria will ensure that the patient is eligible for the extended indication of emicizumab.

In addition, the patient will have to fulfil the following criteria:

- Initiation of emicizumab treatment during the cohort entry period.
- Information on previous HA outcomes and HA treatments approximately 12 months prior to the index date. In case HA diagnosis occurred within 12 months of the index date, the required lookback period will be shortened to time from HA diagnosis to index date. Anamnestic information capturing historic events but entered in the

Hemlibra—F. Hoffmann-La Roche Ltd

Protocol BO44691, Version 2.0

registry database less than 12 months before the index date will be considered as long as they were recorded prior to the index date.

- Information on risk factors of TE events (e.g., medical comorbidities, treatments and demographic characteristics) approximately 12 months prior to the index date. If the patient is below 1 year of age, the lookback period will be shortened to birth until index date. Anamnestic information capturing historic events but entered in the registry database less than 12 months before the index date will be considered as long as they were recorded prior to the index date.
- Signed the informed consent form where required by local regulations.

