4	Varying the definition of severe bleeding phenotype using two definitions based on criteria for which all ingoing registries have coverage of both criteria. These definitions will be applied and analysed in two separate sensitivity analyses:	All data sources do not collect all criteria for severe bleeding phenotype (see Table 6). This can result in selection bias wherein patients are included based on the availability of the differing criteria across data sources. By varying the criteria of the severe bleeding phenotype definition in two sensitivity analyses we will test its robustness and gauge potential selection bias.	This will create similar selection criteria across all registries thus reducing potential differential selection across registries.	All three criteria of severe bleeding phenotype are important thus limiting the definition of severe bleeding phenotype might coincidentally introduce other forms of selection bias. As ABR might require both baseline and follow-up visits in the registry, this could result in a smaller sample size in some data sources. Not all registries will be able to fulfil both criteria (see Table 1 for details).

ABR, Annual Bleeding Rate; AEs, Adverse Events; EU, European Union; ITT, Intention to treat; MA, Market Authorisation.

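### Sensitivity analysis 4 presumes phenotype criteria that every registry covers; its own limitation cell and Table 1 say otherwise, so like-for-like selection across registries is not secured

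*Protocol*

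**What the plan says.** Protocol section 8.2.6.1 lets a patient qualify as having a severe bleeding phenotype through any one of three routes: FVIII prophylaxis in the previous 12 months, a past spontaneous bleed, or an ABR of at least 2 in the previous 12 months. It accepts that "the exact operational definition of the severe bleeding phenotype will vary between data sources", and Table 1 grades how well each registry records each route.

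Section 8.7.4, Table 10, analysis 4 responds to this by varying the phenotype definition in two separate analyses. These are to be "two definitions based on criteria for which all ingoing registries have coverage of both criteria". The strengths cell says: "This will create similar selection criteria across all registries thus reducing potential differential selection across registries". The limitations cell of the same row says: "Not all registries will be able to fulfil both criteria (see Table 1 for details". Section 8.9.1 relies on these two analyses to test how robust the phenotype definition is.

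Two rows of Table 1 matter most. For the UK registry: "UKNHD UK Low Low Derived (number of new bleeding episodes at follow-up". For the US registry: "ATHN dataset US Not collected Good* Derived (bleed events". The legend reads "Good = >70% patients included in the disease registries have the required variable" and "Low <40% patients with variable, Captured = Not disclosed".

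**The concern.** The premise of full coverage and the limitation that denies it cannot both stand in one row. The premise carries weight, because comparable selection across registries follows only if every registry can apply the criteria to most of its patients.

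The stake is how the result can be read. If a definition can be assessed in most patients in some registries and in a minority in another, moving to that definition changes two things at once: the phenotype rule and the share each registry contributes. If the thromboembolic event rate then moves, the reader cannot tell which of the two caused it. That weakens a check that section 8.9.1 puts forward against a selection bias the protocol itself acknowledges.

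**Working it through.** **Inputs.** Coverage grades come from Table 1 (section 8.2.6.1) and moderate HA counts from Table 7 (section 8.4).

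| Registry | Moderate HA | Spontaneous bleeding | Prior prophylaxis | ABR |
|---|---|---|---|---|
| UKNHD | 836 | Low | Low | Derived |
| FranceCoag | 940 | Good | Good | Derived |
| HemoNED | 230 | Captured | Captured | Derived |
| ATHN | 15 | Not collected | Good | Derived |
| WBDR | 2987 | Good | Good | Derived |
| CBDR | 299 | Collected | Good | Derived |

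**Step 1: the plan's total.** 836 + 940 + 230 + 15 + 2987 + 299 = 5307, which matches section 8.4.

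**Step 2: every possible pair.** The two definitions announced in Table 10 do not appear in the text at hand. This is probably a conversion loss and is not held against the plan, so all three pairs are checked.

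- Spontaneous bleeding and prophylaxis: UKNHD is Low on both, and ATHN does not collect the first.
- Spontaneous bleeding and ABR: UKNHD is Low on the first, and ATHN does not collect it.
- Prophylaxis and ABR: UKNHD is Low on the first.

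No pair is free of a Low or Not collected grade. Only ABR on its own is, and its entries carry no completeness figure in any registry.

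**Step 3: weight of the affected registries.** UKNHD: 836 / 5307 = 15.8%. ATHN: 15 / 5307 = 0.28%. UKNHD is the one that matters.

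**Step 4: possible shift in registry mix under a prophylaxis definition (illustration).** Let c be the fraction of UKNHD patients with the variable and g the fraction in each of the other five registries, which together hold 5307 − 836 = 4471 patients. UKNHD's share of assessable patients is 836c / (836c + 4471g). The protocol gives only a ceiling of 40% for c, so 10% is an assumed lower value. For g, 70% is the floor of Good and 100% is full completeness. HemoNED is assumed to lie in that range, although its figure is undisclosed.

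| c | g | Calculation | UKNHD share |
|---|---|---|---|
| 40% | 100% | 334.4 / 4805.4 | 7.0% |
| 40% | 70% | 334.4 / 3464.1 | 9.7% |
| 10% | 100% | 83.6 / 4554.6 | 1.8% |
| 10% | 70% | 83.6 / 3213.3 | 2.6% |

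Against 15.8% in the full pool, the share falls to between 1.8% and 9.7%. These are shares of the registry pool if registry-wide completeness applies to moderate patients. They are not counts of cohort patients.

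**The case against.** Several counter-arguments have force.

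- **Low is not none.** If the pair is prophylaxis and ABR, Table 1 shows some coverage of both in all six registries. Table 1 then contradicts adequate coverage, not any coverage. This stands, but the limitations cell still denies the premise outright, and coverage under 40% in one registry against over 70% in those graded Good does not give comparable selection.
- **Ingoing may mean finally contracted registries.** Participation is conditional on contracting, so the premise might become true later. The row as written still denies it.
- **A reader might infer that a calculable number of UKNHD cohort patients would be lost to missing data.** The documents do not support this. The grades describe whole registries, not emicizumab initiators. Section 8.2.6.1 already requires information on HA treatments for roughly the preceding 12 months, so patients without it should not be in the main cohort, although section 8.9.2 admits this may not always be confirmed.
- **Other evidence on UKNHD is more favourable.** Table 6 grades its HA treatments, which include FVIII, as Good. Table 4 lists reason for treatment as Captured, and section 8.4 says its patient app records treatments and the reasons for them. Prophylaxis might be derivable. This sits uneasily with Low in Table 1 and needs reconciling.
- **A reader might infer that analysis 4 as a whole selects on missing data, or that it is the only check.** The first is a plausible inference for a prophylaxis or spontaneous-bleeding definition but is not shown for ABR. The second is too strong: section 8.7.3 plans subgroups by prior prophylaxis and by region, which help in part but do not supply a common definition.
- **The protocol claims only to reduce differential selection**, and the row itself warns that narrowing the definition could bring in other selection bias. Dropping spontaneous bleeding would also remove one real difference, though ATHN is only 0.28% of the pool.

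**Conclusion.** The point holds as an internal contradiction with a limited consequence. The premise of analysis 4 is denied within its own row, and no pair of criteria in Table 1 supports it at an adequate level. Comparable selection across registries is therefore asserted but not secured.

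Under a definition that uses a Low-coverage criterion, UKNHD (15.8% of moderate patients) could be under-represented because data are missing. A changed rate could then reflect registry mix and not the phenotype rule. The illustrated fall in UKNHD's share to 1.8–9.7% depends on the completeness values assumed above. The number of cohort patients affected cannot be determined from the documents.

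The primary incidence rate is unaffected; what suffers is the value of this analysis as a check on phenotype selection. The row also refers the reader to Table 6 for the phenotype criteria, which are in Table 1.

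**What to change.** In Table 10, analysis 4:

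1. Delete the statement that all registries cover both criteria, and correct the cross-reference from Table 6 to Table 1.
2. Make ABR of at least 2 alone, in all registries, the common-definition analysis. Report ABR completeness by registry, since Table 1 gives none and the row itself warns that ABR may need both baseline and follow-up visits.
3. Run a prior-prophylaxis or spontaneous-bleeding definition only in registries with adequate coverage of that criterion. State the threshold for adequate, and obtain the undisclosed HemoNED figure. Show the result beside the main analysis rerun in the same registries, so that a change of definition is separated from a change of registry mix.
4. Reconcile UKNHD's Low for prophylaxis in Table 1 with its Good for HA treatments in Table 6. If prophylaxis can be derived from treatment records, say so and regrade it.

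The cost is wording in one table row, one rerun of the main analysis and a smaller restricted analysis. If eligible patients are spread as in Table 7, leaving out UKNHD keeps 4471 / 5307 = 84.2%, about 168 of the 200 target patients. Leaving out ATHN as well, for spontaneous bleeding, keeps 4456 / 5307 = 84.0%, also about 168.

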8.7.5. Handling of Missing Data

For the current study, the feasibility assessment has clarified the level of reporting of key study variables (see Table 1, Table 4, Table 5 and Table 6). Methods commonly used in NI studies for handling missing data will be applied. The number of patients with missing data will be reported for each measured variable in the study. For the descriptive tables, missing data will be described separately and not included in the denominator for the calculation of the percentage for each category of a particular variable. Full details on handling of missing data will be described in detail in the SAP.

8.8. DATA QUALITY ASSURANCE AND QUALITY CONTROL

IQVIA will maintain adequate and accurate records to enable the conduct of the study to be fully documented, including but not limited to the protocol, protocol amendments, Informed Consent Forms (if applicable), and documentation of Institutional Review Board/ Independent Ethics Committee (IRB/IEC) and governmental approval or notification (if required).

IQVIA shall ensure that the datasets and statistical programmes used for generating the data included in the final study report are kept in electronic format and are available for auditing and inspection.

Retention of Records

Archiving at the study site has to be for at least 5 years after final study report or first publication of study results, whichever comes later; or according to local regulation.

Records and documents pertaining to the conduct of this study must be retained by MAH for at least 5 years after completion of the study, or for the length of time required by relevant national or local health authorities, whichever is longer. After that period of time, the documents may be destroyed, subject to local regulations.

No records may be disposed of without the written approval of the MAH. Written notification should be provided to the MAH prior to transferring any records to another party or moving them to another location.

Quality Control

The study will be conducted according to the European Network of Centres for Pharmacoepidemiology and Pharmacovigilance (ENCePP) Guide on Methodological Standards in Pharmacoepidemiology, the ENCePP Checklist for Study Protocols, the International Society for Pharmacoepidemiology, Good Pharmacoepidemiology Practice (GPP) Guidelines and IQVIA SOPs. At the study level, all aspects of the study from protocol development to the reporting of the results are conducted within the work frame

of IQVIA Quality Management System and in accordance with the appropriate global procedure.

According to the above-mentioned policies and procedures, Standard procedures will be used to ensure data quality and integrity, including quality checks described in section 8.6. and a QC checklist is developed and executed for the study, which includes QC on study methodology, SAP, programming, data management and analysis, study results, conclusions and study report. Furthermore:

- The study QC plan establishes ownership for the execution of the individual QC steps. The principle of the independence of QC applies.
- Individuals responsible for the execution of specific QC steps must have knowledge, capability and experience which are adequate for the task.
- The result of the execution of the individual steps of the QC plan is documented, and includes the required corrective actions, if any.
- The execution of any required corrective action is documented.

The executed QC plan will be subjected to a final review and approval for sufficiency and completeness by the IQVIA project management team.

The Investigator will comply with the confidentiality policy as described in the site contract, with the requirements described in the protocol. The treating physician is ultimately responsible for the conduct of all aspects of the PASS at the local level and verifies the integrity of all data transmitted to the IQVIA.

In compliance with regulatory requirements, the MAH, a third party on behalf of the Sponsor, or regulatory agencies may conduct quality assurance audits/inspections at any time during or following the study. The investigator must agree to allow auditors/inspectors direct access to all study-related documents, including source documents, and must agree to allocate his or her time and the time of his or her study staff to the auditors/inspectors in order to discuss findings and issues. The protocol, each step of the data capture procedure, and the handling of the data, as well as the eventual study report, will be subject to independent Clinical Quality Assurance.

8.9. LIMITATIONS OF THE RESEARCH METHOD

8.9.1. Selection Bias

There is a possibility of selection bias if the registries to be included cover a select subset of patients that do not represent the overall patient population. However, the selected patient population is in need of specialised haematological care and the likelihood that any of the patient would be treated only in primary care is low as HA patients require specialised care. Another potential source of selection bias is that clinics **Hemlibra—F. Hoffmann-La Roche Ltd** Protocol BO44691, Version

2.0

that are part of networks that report to specialised haemophilia registries might deliver higher quality of care resulting in a better safety profile. Nonetheless, the wide preliminary selection of registries with different coverage and geographical locations should help counter this selection bias.

It is likely that even within the patient group in the study at hand, i.e., patients with congenital HA without FVIII inhibitors who have moderate disease ($1\% \le FVIII \le 5\%$) and severe bleeding phenotype, there will be differences between those who receive emicizumab, compared with those who do not. That is, it is likely that the patients receiving emicizumab would be on the lower end of the FVIII interval closer to 1% with a higher risk of bleeding (Tiede et al., 2021). A thorough patient evaluation will be conducted to investigate the patients included in the study and report these descriptive statistics based on the patient's medical history.

The inclusion criterium for severe bleeding phenotype is based fulfilling either one of three criteria that are based on information regarding previous prophylactic treatment with FVIII infusions, previous spontaneous bleeding events and ABR. All data sources do not collect information regarding all of these criteria and the data sources might have different levels of completeness in the variables underlying the criteria. This can result in selection bias wherein patients in some registries are included based on the availability of the different criteria. To test the robustness of the severe bleeding phenotype definition and the variability in the outcomes that results from this, we will perform 2 sensitivity analyses where the severe bleeding phenotype criteria are varied.

8.9.2. Information Bias

Information bias is the bias arising from the systematic measurement error or misclassification of patients. As this is a registry-based study the validity of the findings of the study will solely rely on the validity, quality and completeness of the information recorded in the registries. There is potential for heterogeneity in the type of data collected from the registries regarding emicizumab treatment exposure, e.g., the exact dates of dispenses and SC injections, that could potentially result in exposure misclassification that are registry specific. Depending on the registry, specific limitations for exposure classification could be developed to avoid misclassification. There is also potential for heterogeneity in the study population because of different lookback periods when patients enrol in different registries. In certain cases, the lookback period might not be fully 12 months and the inclusion criteria regarding previous HA outcomes and HA treatments approximately 12 months prior to the index date (see section 8.2.6.1.) may not be fully confirmed if emicizumab treatment initiation (index date) coincides with patient enrolment into the registry.

In the primary incidence analysis, we do not exclude patients with a history of TE events before the index date. Thus, there exists a possibility that individuals with prior TE **Hemlibra—F. Hoffmann-La Roche Ltd**

Protocol BO44691, Version 2.0 events are included in the crude IR of TE. In the planned analysis of secondary objective 4 the IR would be tabulated based on the history of TE events during the lookback period. This would ensure that the incidence would be calculated for patients treated with emicizumab without any prior TE events during the lookback period and in addition contribute valuable evidence on the event rate among patients treated with emicizumab who have a history of TE events.

When calculating the crude IRs for our safety events of interest, the MAH will also test the possibility of information bias caused by the long-term effects of the treatment and informative censoring. For this, a sensitivity analysis will be performed using an ITT analysis where all patients initiating treatment with emicizumab will be followed until the end of the study period without censoring at emicizumab treatment discontinuation. This is to consider the potential impact of long-term treatment effects even after cessation of the treatment and assess the impact of informative censoring due to patients ending treatment early because of subclinical signs of an AE.

9. PROTECTION OF HUMAN PATIENTS

9.1. INFORMED CONSENT

The MAH will identify whether a new informed consent form is needed for using the data from the registries. For example, in some cases, additional patient informed consent forms or information letters indicating that the data will be transferred to another organisation for analysis may be required and will have to be obtained from individual patients depending on the rules and regulations setup by the data source or local authorities.

In addition to ensuring whether informed consent is needed certain precautions will be taken, including:

- Ensuring data are anonymised / pseudonymised
- Ensuring final analysis data are anonymised / pseudonymised
- Ensuring possibility of linkage back to individual identified patients is impossible or tightly controlled
- Obtaining ethical committee approval for use of data as proposed (e.g., the review of and extraction of information from individual medical charts) records for the proposed use ahead of study initiation

